**Table 11: Analysis Strategy for Safety Parameters**

Safety Endpoint	Number and Percentage of Participants, Number of Events	95% CI
Any solicited AR (overall and by local, systemic)	X	X
Any unsolicited AE	X	—
Any SAE	X	—
Any unsolicited MAAE	X	—
Any unsolicited treatment-related AE	X	—
Any treatment-related SAE	X	—
Discontinuation due to AE	X	—
Any severe AE	X	—
Any treatment-related severe AE	X	—

Abbreviations: AE = adverse event; AR = adverse reaction; CI = confidence interval; MAAE = medically attended adverse event; MedDRA = Medical Dictionary for Regulatory Activities; PT = preferred term; SAE = serious adverse event; SOC = system organ class.

Note: 95% CI using the Clopper-Pearson method. X = results will be provided. Solicited ARs and unsolicited AEs will be summarized by SOC and PT coded by MedDRA.

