**Table 2: Study Objectives and Endpoints**

Objectives	Endpoints
Primary Objectives	Primary Endpoints

To evaluate the safety and reactogenicity of up to 3 dose levels (25, 50, and 100 µg) of mRNA-1273 vaccine administered as 2 doses 28 days apart in 3 age groups

	

Solicited local and systemic ARs through 7 days after each injection

Unsolicited AEs through 28 days after each injection

MAAEs through the entire study period

SAEs through the entire study period

AESIs, including MIS-C and myocarditis and/or pericarditis, through the entire study period

To infer the efficacy of mRNA-1273 (25, 50, and 100 µg, administered as 2 doses 28 days apart) based on immunogenicity in 3 age groups

	

The proportion of participants with a serum antibody level at Day 57 <math>\geq</math> antibody threshold of protection

If an accepted serum antibody threshold of vaccine protection against COVID-19 is available, this analysis will form the basis to infer efficacy

The GM value of serum antibody level and seroresponse rate (SRR) from Study P204 vaccine recipients at Day 57 compared with those from young adult (18 to 25 years of age) vaccine recipients (Day 57) in the clinical endpoint efficacy trial (Study P301)

If a threshold is not available, efficacy will be inferred by establishing noninferiority for each age group (6 years to < 12 years, 2 years to < 6 years, and 6 months to < 2 years in Study P204) compared with 18- to 25-year old participants (Study P301) by both GM value of serum antibody levels and SRR.

For Part 3, the GM value of serum antibody level and SRR from Study P204 vaccine recipients at Day 57 compared with those from adult (<math>\geq</math> 18 years of age)

Objectives	Endpoints
	
vaccine recipients (Day 57) in the clinical endpoint efficacy trial (Study P301)
 
 
• Seroresponse is defined as a titer change from baseline (pre-Dose 1) below the LLOQ to <math>\geq 4 \times</math> LLOQ, or at least a 4-fold rise if baseline is <math>\geq</math> LLOQ
 

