Any solicited AR that meets any of the following criteria must be entered into the participant's source document and must also be recorded by the study site staff on the solicited AR page of the participant's eCRF:

- Solicited local or systemic AR that results in a visit to a healthcare practitioner (HCP; otherwise meets the definition of an MAAE)
- Solicited local or systemic AR leading to the participant withdrawing from the study or the participant being withdrawn from the study by the investigator (AE leading to withdrawal)
- Solicited local or systemic AR lasting beyond 7 days after injection
- Solicited local or systemic AR that leads to participant withdrawal from IP

- Solicited local or systemic AR that otherwise meets the definition of an SAE

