#### 7.4.4 Medically Attended Adverse Events

An MAAE is an AE that leads to an unscheduled visit to an HCP. This would include visits to a study site for unscheduled assessments (eg, abnormal laboratory test result follow-up, COVID-19 [[Section 7.3.1](#)]) and visits to HCPs external to the study site (eg, urgent care, primary care physician). Investigators will review unsolicited AEs for the occurrence of any MAAE. Unsolicited AEs will be captured on the AE page of the eCRF.

While COVID-19 surveillance is ongoing, all confirmed symptomatic COVID-19 cases ([Section 7.3.1](#)) will be recorded as MAAEs. Any severe COVID-19 cases will be reported to the Sponsor or designee immediately and in all circumstances within 24 hours, using the SAE Mailbox, the SAE Hotline, or the SAE Fax line ([Section 7.4.11](#)). The investigator will submit any updated COVID-19 case data to the Sponsor within 24 hours of it being available.

Once COVID-19 surveillance is discontinued, COVID-19 related AEs will be reported per standard AE reporting for the respective SoA.

All suspected cases of anaphylaxis should be recorded as MAAEs and reported as an SAE, based on criteria for a medically important event, unless the event meets other serious criteria. As an SAE, the event should be reported to the Sponsor or designee immediately and in all circumstances within 24 hours as per [Section 7.4.11](#). The investigator will submit any updated anaphylaxis case data to the Sponsor within 24 hours of it being available. For reporting purposes, a participant who displays signs/symptoms consistent with anaphylaxis as described below should be reported as a potential case of anaphylaxis. This is provided as general guidance for investigators and is based on the Brighton Collaboration case definition ([Rüggeberg et al 2007](#)).

Anaphylaxis is an acute hypersensitivity reaction with multi-organ-system involvement that can present as, or rapidly progress to, a severe life-threatening reaction. It may occur following exposure to allergens from a variety of sources.

Anaphylaxis is a clinical syndrome characterized by:

Sudden onset AND

Rapid progression of signs and symptoms AND

Involves 2 or more organ systems, as follows:

- **Skin/mucosal:** urticaria (hives), generalized erythema, angioedema, generalized pruritus with skin rash, generalized prickle sensation, red and itchy eyes

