### 8.5.2 Safety Analyses

All safety analyses will be based on the Safety Set, except summaries of solicited ARs, which will be based on the Solicited Safety Set. All safety analyses will be provided by vaccination group (dose levels of mRNA-1273 and placebo) and by age group. Participants in Part 1 and Part 2 of the study and in different age groups who receive the same mRNA-1273 dose level may be combined for safety analysis.

Safety and reactogenicity will be assessed by clinical review of all relevant parameters including solicited ARs (local and systemic events), unsolicited AEs, SAEs, MAAEs, AESIs, AEs leading to discontinuation, and physical examination findings.

The number and percentage of participants with any solicited local AR, with any solicited systemic AR, and with any solicited AR during the 7-day follow-up period after each injection by toxicity grade will be provided. A 2-sided 95% exact CI using the Clopper-Pearson method will also be provided for the percentage of participants with any solicited AR.

The number and percentage of participants with unsolicited AEs, SAEs, MAAEs, severe AEs, and AEs leading to discontinuation from IP or withdrawal from the study will be summarized. Unsolicited AEs will be presented by MedDRA preferred term and system organ class.

The number of events of solicited ARs, unsolicited AEs/SAEs, and MAAEs will be reported in summary tables accordingly.

Solicited AR events (starting within 7 days after any injection) that are serious or lasting beyond Day 7 after any injection will also be reported as unsolicited AEs.

For all other safety parameters, descriptive summary statistics will be provided, and [Table 11](#) summarizes the analysis strategy for safety parameters. Further details will be described in the SAP.

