5. Post-dosing, participants will have a 30-minute observation period. If any concerning symptoms occur, investigator may check vital signs during this period (however, no routine vital signs necessary after vaccination if no concerning symptoms).
6. An unscheduled visit may be prompted by reactogenicity issues, or new or ongoing AEs.
7. The nasal swab sample must be collected prior to injection at the BD-1 visit.
8. Trained study personnel will call all participants to collect information relating to any MAAEs (including any signs and symptoms of COVID-19), AESI, AEs leading to withdrawal, SAEs, information on concomitant medications associated with those events, and any non-study vaccinations. Any solicited AR or AE that meets any of the following criteria must be entered into the participant's eCRF:1) An Event, including local or systemic AR, that results in a visit to a healthcare practitioner (HCP) (MAAE). 2) An Event, including local or systemic AR, leading to the participant withdrawing from the study or the participant being withdrawn from the study by the Investigator (AE leading to withdrawal) 3) An Event, including local or systemic AR, that otherwise meets the definition of an SAE. 4) Any AESI.
9. All concomitant medications relevant to or for the treatment of an SAE, AESI, or MAAE will be recorded from screening through the final visit. Non-study COVID-19 vaccines will be recorded through EOS.

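### Table 11 limits the MAAE summary to unsolicited events, which is narrower than the primary endpoint, the MAAE definition and the text of Section 8.5.2

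*Protocol*

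**What the plan says.** - **Endpoint.** Table 2 (Section 2) lists "MAAEs through the entire study period" as a primary safety endpoint for the primary series, for the mRNA-1273 booster or third dose, and for the mRNA-1273.214 booster. There is no restriction to unsolicited events.
- **Definition.** Section 7.4.4: "An MAAE is an AE that leads to an unscheduled visit to an HCP". Solicited reactions are not excluded. The same section then says how MAAEs are found: "Investigators will review unsolicited AEs for the occurrence of any MAAE".
- **Solicited reactions.** The list after Table 9 in Section 7.4.3 names the reactions that need extra recording. Its first item is "Solicited local or systemic AR that results in a visit to a healthcare practitioner (HCP; otherwise meets the definition of an MAAE". Such a reaction "must also be recorded by the study site staff on the solicited AR page of the" participant's eCRF.
- **Analysis text.** Section 8.5.2 twice names MAAEs as an item of their own, once for participants and once for events, with no limit to unsolicited ones. It also carries some solicited reactions over: those "that are serious or lasting beyond Day 7 after any injection will also be reported as unsolicited AEs". Medical attendance is not a trigger.
- **Analysis table.** Table 11, which Section 8.5.2 presents as its summary of the strategy for safety parameters, has the row "Any unsolicited MAAE". The rows for SAEs and for severe AEs carry no such qualifier.
- **mRNA-1273.214.** Section 7.4.3 states that no eDiary is used and that reactions are reported only if attended, serious or leading to discontinuation. Footnote 8 of Table 19 requires eCRF entry of "An Event, including local or systemic AR, that results in a visit to a healthcare practitioner (HCP) (MAAE").

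**The concern.** A primary safety endpoint should be counted as it is defined. Here the definition takes in solicited reactions that send a child to a doctor or urgent care, while the table that sets out the analysis takes in only unsolicited events. The events in between start within a week of injection and are of the kinds expected after vaccination; Section 7.4.3 treats all solicited reactions as related to the product. Whether a reaction needed medical attention is also what the MAAE endpoint adds to a tally of reactions by grade. If the programmed tables follow Table 11, the reported MAAE percentages will be too low against the protocol's own definition, and a reader could not tell this from the table.

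**Working it through.** No figure is at issue and there is nothing to recompute. The check is to follow a medically attended reaction through the rules and see where it is counted.

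**Step 1: when is an event unsolicited?** Section 7.4.1 calls an AE unsolicited if it is not one of the listed solicited terms, or if it is a listed term that starts outside the injection day and the 6 days after it.

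**Step 2: sort the attended events.**

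| Medically attended event | MAAE under 7.4.4 | In the Table 11 row |
|---|---|---|
| (a) Not a listed solicited term, any onset | Yes | Yes, unsolicited under 7.4.1 |
| (b) Listed term, onset after the 7-day window | Yes | Yes, unsolicited under 7.4.1 |
| (c) Listed term, onset in the window, serious or lasting beyond Day 7 | Yes | Yes, by the carry-over rule in 8.5.2 |
| (d) Listed term, onset in the window, non-serious, not lasting beyond Day 7 | Yes, where the visit was unscheduled | **No** |

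Only (d) is lost, and only under Table 11. Under the unrestricted wording in the text of 8.5.2 it would be counted.

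**Step 3: can (d) occur?** Yes. In Tables 8 and 9 many Grade 4 categories are defined by an emergency room visit or hospitalization, and a footnote counts urgent care as an emergency room visit. The hospitalization criterion for an SAE in Section 7.4.2 generally needs at least one overnight stay, so such a visit need not make the event serious. Fever is graded by temperature alone, so a child taken to a doctor for a fever of Grade 1 to 3 that settles within the week also falls in (d).

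**Step 4: where else does (d) appear?** After mRNA-1273 or placebo doses with an eDiary, it appears in the solicited reaction tables. Section 8.5.2 sets these out by toxicity grade, with no display of medical attendance.

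**Step 5: the mRNA-1273.214 booster.** Table 2 gives this product four primary safety endpoints: MAAEs, SAEs, AESIs and AEs leading to discontinuation from the study. With no eDiary there is no routine solicited data. A listed reaction that starts within 7 days and leads to a visit is labelled an MAAE by footnote 8 of Table 19, yet it is not unsolicited under 7.4.1. Read literally, Table 11 drops it, and no eDiary-based solicited table is there to pick it up.

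**Step 6: size.** The number in (d) would be needed by group. The protocol gives no rate of medically attended solicited reactions in any group, so the undercount cannot be computed.

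**The case against.** The best defence is that the text of Section 8.5.2 is unrestricted. It names MAAEs twice, and for events it sets them apart from unsolicited AEs and SAEs. Table 11 is only a summary, and further detail is left to the SAP, which is not at hand. This stands so far as it goes: a reader might take the table as a settled exclusion, and the documents do not support that. What they show is a conflict between text and table. The defence does not remove the conflict, because the sentence in 7.4.4 on finding MAAEs among unsolicited AEs points the same way as the table, and the carry-over rule does not mention attendance.

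The events are also not hidden. Solicited reactions are reported by grade and group, they are the only Table 11 row with a confidence interval, and pause rule 2 in Table 5 covers Grade 4 AEs that cannot reasonably be put down to another cause. That stands too. What is missing is their count as MAAEs, and after mRNA-1273.214 possibly any summary.

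Three stronger readings are tempting and fail:

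- **All medically attended reactions of the first week are lost.** Cases (a) and (c) above are counted.
- **A randomised comparison is biased.** MAAEs are summarised as counts and percentages by group, without a confidence interval, test or planned contrast. Nor can an excess be inferred from assumed rates. For example, 0.5% to 2% on vaccine against 0.2% to 0.5% on placebo, neither of which comes from the protocol, allows anything from 0.5 − 0.5 = 0 to 2 − 0.2 = 1.8 percentage points.
- **The two vaccines have two MAAE definitions.** Section 7.4.3 and footnote 8 of Table 19 both treat an attended reaction as meeting the MAAE definition, and 7.4.4 covers all products. What differs is data capture.

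**Conclusion.** The point holds as an internal conflict on a primary safety endpoint. The Table 11 row is narrower than Table 2, Section 7.4.4, Section 7.4.3 and the text of 8.5.2. If the row governs, listed solicited reactions that are medically attended, non-serious and not prolonged beyond Day 7 are missing from the MAAE summary, and after mRNA-1273.214 they may be missing from every summary. The direction is certain: following the table can only lower the MAAE count. The size is unknown.

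The conclusion assumes that the table would be programmed as labelled and that a listed term starting in the 7-day window stays solicited even when no eDiary is in use, as Section 7.4.1 literally says. The correction is worth making because it changes what a primary endpoint counts. It does not put any hypothesis test in doubt.

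**What to change.** 1. In Table 11, change the row to *Any MAAE*, shown overall and split into solicited and unsolicited.
2. In Section 8.5.2, state that medically attended solicited reactions count in that row. Do not do this by adding attendance to the carry-over sentence: that sentence feeds the unsolicited AE tables, so the row for any unsolicited AE would rise as well.
3. In Section 7.4.4, align the sentence that looks for MAAEs only among unsolicited AEs, so that attended entries on the solicited reaction page are reviewed too.
4. Say that the same rule applies to mRNA-1273, placebo and mRNA-1273.214.

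The cost is one table row with a split, two sentences and slightly higher reported MAAE rates. One thing should be confirmed first. Section 7.4.3 gives several reasons for entering a reaction on the solicited page but does not say that the page records which reason applied. If it does not, attendance would have to be taken from source documents.

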### 8.5.3 Immunogenicity Analyses

The primary analysis population for immunogenicity will be the PP Immunogenicity Subset, unless specified otherwise. The primary objective of this study is to use the immunogenicity response to infer efficacy in participants aged 6 months to < 12 years at the dose level selected for expansion. For this objective, analyses of immunogenicity will be performed for each pediatric age group separately at the selected dose level based on the participants in the PP Immunogenicity Subset. For each pediatric age group, participants in the applicable study part in the PP Immunogenicity Subset may be used for immunogenicity primary analysis. Participants

from Part 1 and Part 2 who receive the same mRNA-1273 dose level selected for expansion may be combined for immunogenicity analyses. If the same dose level is selected for expansion for more than one age group, these age groups may be combined for immunogenicity analyses.

An accepted antibody threshold of protection against COVID-19 may be available based on data from other mRNA-1273 studies or external data. If such a threshold of protection against COVID-19 is available, the number and percentage of participants with antibody greater than or equal to the threshold at Day 57 will be provided with a 2-sided 95% CI using the Clopper-Pearson method. For an age group, if the lower bound of the 95% CI on the mRNA-1273 group is > 70%, the primary immunogenicity endpoint of this study will be considered to be met for that age group.

The number and percentage of participants with serum antibody greater than or equal to the threshold with 2-sided 95% CI will be provided at each postbaseline time point. The CI will be calculated using the Clopper-Pearson method.

If an accepted serum antibody threshold of protection against COVID-19 is not established, immune response as measured by GM value and SRR in each age group based on Day 57 antibody levels will be compared with that in young adults (18 to 25 years of age) using data from Study P301. An analysis of covariance model will be carried out with antibody at Day 57 as dependent variable and a group variable (a pediatric age group in Study P204 versus young adults [18 to 25 years of age] in Study P301) as the fixed variable for each pediatric age group. The GM values of the pediatric age group at Day 57 will be estimated by the geometric least square mean (GLSM) from the model. The GMR (ratio of GM values) will be estimated by the ratio of GLSM from the model. The corresponding 2-sided 95% CI will be provided to assess the difference in immune response between the pediatric age group (Study P204) compared with the young adults (18 to 25 years of age) in Study P301 at Day 57. For each pediatric age group, the noninferiority of GM value will be considered demonstrated if:

- The lower bound of the 95% CI of the GMR is  $\geq 0.67$  based on the noninferiority margin of 1.5, AND
- The GMR point estimate  $> 0.8$  (minimum threshold).

For Part 1 or Part 2 booster dose primary immunogenicity analysis of GM in children receiving mRNA-1273 booster dose, an analysis of covariance model will be performed to assess the difference in the immune response (Ab level) between BD-Day 29 in children receiving mRNA-1273 booster dose (third dose) in Study P204 and Day 57 in young adults ( $\geq 18-25$  years of age) receiving mRNA-1273 primary series in Study P301. In the analysis of covariance model, antibody titers at BD-Day 29 in P204 children and titers at Day 57 in P301 young adults will be a dependent variable, and a group variable (children in Study P204 and young adults in Study

P301) will be the fixed effect. The GMT will be estimated by the GLSM from the model, and its corresponding 95% CI will be provided for each group. The GMR (ratio of GMTs) for children in Study P204 with respect to young adults in Study P301 will be estimated by the ratio of GLSM from the model, and the corresponding 95% CIs will be provided. The 95% CI for GMR will be used to assess the between-group difference in immune response at BD-Day 29 in children in Study P204 compared with Day 57 after the primary vaccine series in young adults in Study P301. The noninferiority of post-booster GM in children will be considered demonstrated if the lower bound of the 95% CI of the GMR is  $\geq 0.67$  based on the noninferiority margin of 1.5.

For Part 3 primary series primary immunogenicity analysis of GM in children 6 years to < 12 years of age receiving mRNA-1273 25  $\mu$ g which is half of the 50  $\mu$ g dose level used in Part 2 for the same age group, the noninferiority hypothesis testing of GM in children compared with adults  $\geq 18$  years of age from Study P301 will be performed using an analysis of covariance model as described above. The noninferiority of GM in children in Part 3 will be considered demonstrated if the lower bound of the (1-alpha) CI of the GMR is  $\geq 0.67$  based on the noninferiority margin of 1.5, where the 1-alpha can be 97.5% or 95% depending on the alpha level of 0.025 or 0.05 used for the hypothesis testing. A sensitivity analysis may be conducted by using different age group(s) (eg, 18 to 25 years,  $\geq 65$  years) from Study P301 as a comparator.

For Part 3 third dose primary immunogenicity analysis of GM in children receiving a third mRNA-1273 dose, an analysis of covariance model will be performed to assess the difference in the immune response at BD-Day 29 between children receiving mRNA-1273 third dose in Study P204 and adults ( $\geq 18$  years of age) receiving mRNA-1273 booster dose (third dose) in Study P301. In the analysis of covariance model, antibody titers at BD-Day 29 in P204 children and titers at Day 57 in P301 young adults will be a dependent variable, and a group variable (children in Study P204 and adults in Study P301) will be the fixed effect. The GMT will be estimated by the GLSM from the model and its corresponding 95% will be provided for each group. The GMR for children in Study P204 with respect to adults in Study P301 will be estimated by the ratio of GLSM from the model and the corresponding 95% CIs will be provided. The 95% CI for GMR will be used to assess the between-group difference in immune response at BD-Day 29 in children in Study P204 compared with Day 57 following the primary vaccine series in adults in Study P301. The noninferiority of post-third dose GM in children will be considered demonstrated if the lower bound of the (1-alpha) CI of the GMR is  $\geq 0.67$  based on the noninferiority margin of 1.5.

The number and percentage of participants with seroresponse due to vaccination will be provided with 2-sided 95% CI using the Clopper-Pearson method at each postbaseline time point with Day 57 being of the primary interest in the analyses for the mRNA-1273 primary series in Part 1

or Part 2. The SRR difference with 95% CI (using Miettinen-Nurminen score method) at Day 57 will be provided between children receiving mRNA-1273 primary series in Study P204 Part 1 or Part 2 and young adults of 18 to 25 years of age receiving mRNA-1273 primary series in Study P301. For each pediatric age group in Part 1 or Part 2, the noninferiority of SRR will be considered demonstrated if:

- The lower bound of the 95% CI of the SRR difference is  $\geq -10\%$  based on the noninferiority margin of 10%, AND
- The SRR difference point estimate  $\geq -5\%$  (minimum threshold).

For Part 1 or Part 2 booster dose primary immunogenicity analysis of seroresponse in children receiving mRNA-1273 booster dose (as applicable), the SRR with 95% CI (using Clopper-Pearson method) will be summarized. The SRR difference with 95% CI (using Miettinen-Nurminen score method) to compare post-booster SRR at BD-Day 29 in children in Study P204 with the primary series SRR at Day 57 (28 days after Dose 2) in adults (18 to 25 years of age) in Study P301 will be computed. The SRR is defined as a titer change from baseline (pre-Dose 1) below the LLOQ to  $\geq 4 \times$  LLOQ, or at least a 4-fold rise if baseline is  $\geq$  LLOQ. The noninferiority of SRR in children receiving mRNA-1273 booster dose will be considered demonstrated if the lower bound of the 95% CI of the SRR difference is  $\geq -10\%$  based on the noninferiority margin of 10%.

For Part 3 primary series primary immunogenicity analysis of seroresponse in children 6 to < 12 years of age receiving mRNA-1273 25  $\mu$ g which is half of the 50  $\mu$ g dose level used in Part 2 for the same age group, the noninferiority hypothesis testing of SRR in children compared with adults  $\geq 18$  years of age from Study P301 will be performed using the analysis of SRR as described above. The SRR difference with (1-alpha) CI at Day 57 will be provided between children receiving mRNA-1273 primary series in Study P204 Part 3 and adults of  $\geq 18$  years of age receiving mRNA-1273 primary series in Study P301. The 1-alpha can be 97.5% or 95% depending on the alpha level of 0.025 or 0.05 used for the hypothesis testing. The noninferiority of SRR in children receiving mRNA-1273 25  $\mu$ g primary series in Part 3 will be considered demonstrated if the lower bound of the (1-alpha) CI of the SRR difference is  $\geq -10\%$  based on the noninferiority margin of 10%. A sensitivity analysis may be conducted by using different age group(s) (eg, 18 to 25 years,  $\geq 65$  years) from Study P301 as a comparator.

For Part 3 third dose primary immunogenicity analysis of seroresponse in children receiving a third dose of mRNA-1273, the SRR with (1-alpha) CI (using Clopper-Pearson method) will be summarized, where the 1-alpha can be 97.5% or 95% depending on the alpha level of 0.025 or 0.05 used for the hypothesis testing. The SRR difference with (1-alpha)% CI (using Miettinen-Nurminen score method) to compare post-third dose SRR at BD-Day 29 in children in Study P204 with the primary series SRR at Day 57 (28 days after Dose 2) in adults ( $\geq 18$  years of

age) in Study P301 will be computed. The SRR is defined as a titer change from baseline (pre-Dose 1) below the LLOQ to  $\geq 4 \times$  LLOQ, or at least a 4-fold rise if baseline is  $\geq$  LLOQ. The noninferiority of SRR in children receiving a third dose of mRNA-1273 in Part 3 will be considered demonstrated if the lower bound of the (1-alpha) CI of the SRR difference is  $\geq -10\%$  based on the noninferiority margin of 10%.

In addition, the GM value of anti-SARS-CoV-2-specific antibody with corresponding 95% CI will be provided at each time point. The 95% CIs will be calculated based on the t-distribution of the log-transformed values then back transformed to the original scale. For each age group, the geometric mean fold-rise (GMFR) of specific nAb and bAb with corresponding 95% CI at each postbaseline time point over preinjection baseline at Day 1 and an earlier time point if applicable will be provided. Descriptive summary statistics including median, minimum, and maximum will also be provided.

